Despite the significant advances in trauma care delivery and post-injury management practices which have occurred over the last decade, uncontrolled hemorrhage remains one of the leading causes of trauma related deaths.^{4,5,87,88} Recent evidence demonstrates that the early use of the antifibrinolytic agent tranexamic acid after trauma center arrival results in improved survival in patients at risk for bleeding.⁴¹ Bringing this proven treatment to the prehospital arena and intervening earlier in those patients who would otherwise not be candidates for treatment has the real potential to further reduce or prevent the vicious hemorrhagic cascade, improve clinical outcomes and provide insight into the underlying mechanisms responsible for and which maximize its benefit. This potential knowledge base would be dramatically beneficial to both military and civilian trauma systems. It is in both these settings where the prehospital phase of treatment represents a relatively novel arena for new interventions. The results provided by the successful completion of this proposal will have paramount implications for both military and civilian injured patients as control of hemorrhage and delay to definitive care represent major impediments for both populations. This proposal will provide needed insight into the consequences of early tranexamic acid intervention in these significantly injured patients when these impediments exist.

H. Research Design and Methods

H.1. Study Design/Setting: The study will be a 3 year, multi-center, blinded, randomized trial utilizing level-1 trauma centers with busy emergency medical transport services with a clinical research track record. For patients at risk of hemorrhage being transported by emergency medical transport, the infusion of 1 gram of tranexamic acid over approximately 10 minutes in the prehospital setting will be compared to placebo. The University of Pittsburgh Medical Center (UPMC) will be both the clinical outcome and data coordinating center. Each individual institution will perform point of care rapid TEG analysis and coagulation measurements on site. UPMC presbyterian is the busiest level-1 trauma center in the state of Pennsylvania and is affiliated with the largest non-profit air medical service in the country with an extensive track record of multi-center, in-

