hospital and prehospital clinical trials. All enrolling centers and respective investigators similarly have busy emergency medical services and significant experience with multi-center trials, the research infrastructure to allow them to successfully occur and have no other clinical investigations that would preclude participation in the current proposal. *Participating Institutions include: University of Pittsburgh, University of Arizona, University of Texas at San Antonio, and the University of Utah. The University of Tennessee at Memphis will be utilized as an alternate/additional site if required.*

H.2. Study Population: The study population will include blunt or penetrating injured patients at risk of hemorrhage being transported via emergency medical services from the scene of injury or from referring hospital to a definitive trauma center that is participating in the trial. We have selected similar inclusion criteria as the prior large, prospective study⁴¹ (CRASH-2). This represents a similar level of acuity than the CRASH-2 study and additionally allows the mechanism of tranexamic acid's benefit to be characterized across a spectrum of injury severity since the pre-specified analysis of the CRASH-2 trial demonstrated that the mortality benefit attributable to early tranexamic acid remained consistent across patients with low thru high predicted mortality, suggesting its use should not be limited to the most severely injured.⁴⁴ The study group may also contain traumatic brain injured patients who represent a subgroup that may also benefit from early tranexamic intervention.⁴⁵ Based upon our own current data (2011-2012) in injured patients that require air medical transport, these inclusion criteria are associated with over a 65% blood transfusion rate in the first 24 hours from admission and represents the most pertinent population for the trial.

H.2.1. Specific Inclusion Criteria:

1. Blunt or penetrating injured patients at risk of hemorrhage being transported via emergency medical services from the scene of injury or from referring hospital to a definitive trauma center that is participating in the trial

AND

2. Within 2 hours of estimated time of injury

AND

3A. Hypotension (Systolic Blood Pressure (SBP) < 90mmHg)

i. At scene of injury or during emergency medical transport

ii. Documented at referring hospital prior to emergency medical transport arrival

OR

3B. Tachycardia (heart rate >110 beats per minute)

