i. At scene of injury or during emergency medical transport

ii. Documented at referring hospital prior to emergency medical transport arrival

H.2.2 Specific Exclusion Criteria:

1. Age > 90 or < 18 years of age; **2.** Inability to obtain intravenous or intraosseous access;**3.**

Documented (radiographic evidence) cervical cord injury with motor deficit; **4.** Known prisoner; **5.**

Known pregnancy; **6.** Traumatic arrest with > 5 minutes CPR without return of vital signs; **7.**

Penetrating cranial injury **8.** Traumatic brain injury with brain matter exposed; **9.** Isolated drowning or

hanging victims **10.** Wearing an opt out bracelet. **11.** Objection to study voiced by subject or family

member at the scene. **12.** Isolated fall from standing

Inclusion and exclusion criteria will be assessed based on available information at the time of enrollment. Although all reasonable efforts will be made by the emergency medical crew to either directly witness or obtain documentation of inclusion criteria, including qualifying vitals, due to the nature of the emergency pre-hospital setting, there may be occasions where the emergency medical crew must rely on verbal report of qualifying vitals from the referring hospital or ground crew. In these instances, if, after subsequent review of outside hospital and/or ground crew documentation, it is determined that the subject did not meet inclusion criteria

and/or met exclusion criteria, the subject will remain enrolled in the study based on the intention-to-treat principle.

In the event that a verbal report must be used in lieu of physical documentation or directly witnessing the qualifying vitals, documentation of the verbal report will serve as the source documentation for determining eligibility. Verbal reports will be documented in the emergency medical record and will detail the information reported and by whom.

H.3. Interventional Arm: The Intervention will have both a prehospital phase and in-hospital phase. Investigational Drug Services (IDS) at the University of Pittsburgh will be utilized to supply and organize both tranexamic acid and placebo along with respective normal saline bolus and infusion bags to all participating trial sites. IDS at the University of Pittsburgh has a long track record of managing large multicenter trials and is currently executing and responsible for over 150 inpatient and outpatient clinical trials.

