We will inform the family member or LAR at the earliest feasible opportunity of the subject's inclusion in the clinical trial, the details of the trial, other information contained in the informed consent document, and that he or she may discontinue the subject's participation at any time without penalty or loss of benefits to which the subject is otherwise entitled. The therapeutic window for this trial is zero due to prehospital nature of this trial. Such notification is not usually feasible before or at the actual time of treatment or trial enrollment and must be deferred until after resuscitation efforts have been completed. Such notification will be in person wherever possible and as soon as feasible (unless otherwise directed by a local IRB). A log will be kept to document the attempts made to contact the LAR/family member. The log will be included in the paper data collection forms.

The investigators will utilize social workers and law enforcement personnel to try to locate the patient's legally authorized representative. If that search is unsuccessful, a notification letter will be sent to the subject's authorized representative explaining the study and providing contact information for answering questions. The letter will be sent via registered mail or by UPS and documentation of the addressee and date of mailing will be kept.

N. Data

N.1. Sources: Data will be collected prospectively as patient care progresses. This will include a review of the emergency medical patient care report(s), Emergency Department and electronic/ paper hospital records.

N.2. Prehospital Resuscitation Elements: Demographics, emergency medical response times (call receipt to arrival, arrival at patient side,) injury characteristics, vital signs, prehospital resuscitation characteristics, (plasma volume, crystalloid volume, blood transfusion volume, starting at referring hospital or scene) prehospital interventions (needle decompression, chest tubes) referring hospital vitals, and interventions.

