Inc Power: These are the amounts that are added to the total power at each interim test. They are often called the exit probabilities because they give the probability that significance is found and the trial is stopped, given the alternative hypothesis.

O’Brien-Fleming boundary values are inversely proportional to the square root of information levels on the standardized Z scale (O’Brien and Fleming 1979). The O’Brien-Fleming boundary is conservative in the early stages and tends to stop the trials early only with a small P -value. But the nominal value at the final stage is close to the overall P -value of the design.

The above plot shows the interim boundaries for each look. This plot shows very dramatically that the results must be extremely significant at early looks, but that they are near the single test boundary (1.96 and -1.96) at the last look.

Interim Analysis References

2. Lan, K.K.G. and DeMets, D.L. 1983. 'Discrete sequential boundaries for clinical trials.' *Biometrika*, 70, pages 659-663.
3. O'Brien, P.C. and Fleming, T.R. 1979. 'A multiple testing procedure for clinical trials.' *Biometrics*, 35, pages 549-556
4. Pocock, S.J. 1977. 'Group sequential methods in the design and analysis of clinical trials.' *Biometrika*, 64, pages 191-199

P.5 IP Stopping Rules: Study product administration should not be stopped except for in the rare instance that necessary treatment or clinical condition would be contraindicated to TXA administration, patient has a confirmed (as determined by an attending physician) seizure during administration, or if the patient is experiencing a suspected allergic reaction to the study product.

Q. Quality Control and Assurance

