1. Blunt or penetrating injured patients being transported via emergency medical services from the scene of injury or from referring hospital to a definitive trauma center that is participating in the trial

AND

2. Within 2 hours of time of injury

AND

3A. Hypotension (Systolic Blood Pressure (SBP) < 90mmHg)

i. At scene of injury or during emergency medical transport

ii. Documented at referring hospital prior to emergency medical transport arrival

OR

3B. Tachycardia (heart rate >110 beats per minute)

i. At scene of injury or during emergency medical transport

ii. Documented at referring hospital prior to emergency medical transport arrival

Inclusion criteria #3. and #4. not required to be simultaneous

Exclusion Criteria:

1. Age > 90 or < 18 years of age;

2. Inability to obtain intravenous or intraosseous access ;

3. Documented cervical cord injury with motor deficit;

4. Known prisoner;

5. Known pregnancy;

6. Traumatic arrest with > 5 minutes CPR without return of vital signs;

7. Penetrating cranial injury

8. Traumatic brain injury with brain matter exposed;

9. Isolated drowning or hanging victims

10. Wearing an opt out bracelet.

11. Isolated fall from standing

12. Objection by patient or family member

Interventional Arm: The Intervention will have both a prehospital phase and in-hospital phase. Investigational Drug Services (IDS) at the University of Pittsburgh will be utilized to supply and organize both tranexamic acid and placebo along with respective normal saline bolus and infusion bags to all participating trial sites. IDS at the University of Pittsburgh has a long track record of managing large multicenter trials and is currently executing and responsible for over 150 inpatient and outpatient clinical trials.

Prehospital Phase Intervention: Once inclusion and exclusion are verified while the patient is being transported via emergency medical transport to a STAAMP trial participating center, in a randomized, double blinded fashion, either 1 gram bolus of tranexamic acid diluted in 100cc of normal saline (preprepared on helicopter) or placebo of identical volume will be infused into the patient over approximately 10 minutes. After receiving the prehospital phase intervention, standard operating procedures utilizing goal directed crystalloid infusion will be followed

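### Patients already given tranexamic acid for this injury are not excluded, so some placebo patients can enter already treated

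*Combined protocol and SAP*

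**What the plan says.** - **Who enters.** H.2.1 takes patients transported "from the scene of injury or from referring hospital to a definitive trauma center that is participating in the trial", within 2 hours of estimated injury. Hypotension or tachycardia documented at the referring hospital before the transport crew arrives is enough to qualify.
- **Who is kept out.** H.2.2 has 12 exclusions, from "Age > 90 or < 18 years of age" to "Isolated fall from standing". The DSMB charter (Appendix 3) also has 12, ending with "Objection by patient or family member". Neither list mentions TXA already given or a contraindication to TXA.
- **Why the trial is done.** Section G gives the aim as "Bringing this proven treatment to the prehospital arena and intervening earlier in those patients who would otherwise not be candidates for treatment".
- **What is recorded.** N.2 lists fluid and blood product volumes from the scene or referring hospital onward, then "prehospital interventions (needle decompression, chest tubes) referring hospital vitals, and interventions". N.3 lists emergency department and operative interventions. TXA is not named in either.
- **How patients are analysed.** Section J and J.1.1 include everyone randomised, by assigned arm. J.5 keeps patients later found ineligible in their randomised group.
- **When product stops.** P.5 allows administration to stop in the rare instance that "necessary treatment or clinical condition would be contraindicated to TXA administration", for a confirmed seizure during administration, or for a suspected allergic reaction.

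**The concern.** The protocol regards in-hospital TXA as effective and aims to bring it to patients who would not otherwise receive it in time. A patient treated at a referring hospital or by an earlier crew falls outside that rationale but is eligible as written.

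Two comparisons are affected. For the primary endpoint, a placebo patient who has had TXA is a treated patient counted as a control, and the mortality difference moves toward zero. For Aim 4, the three in-hospital regimens differ by 1 g steps, so one extra gram from outside the study can move a patient from one planned total to the next. Arrival hyperfibrinolysis and the scene-versus-referral subgroup in J.4 are exposed too, because earlier TXA could act before the arrival sample and can arise at the referring hospital.

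**Working it through.** **1. Is the omission real?** Read side by side, the two exclusion lists cover age, vascular access, cervical cord injury, prisoner status, pregnancy, prolonged arrest, penetrating cranial injury, exposed brain matter, drowning or hanging, opt-out bracelet, objection, and fall from standing. Neither covers prior TXA. H.7 and H.8 deal with crystalloid and transfusion, and J.6 with wrong treatment packs. No other section available for review restricts or accounts for non-study TXA.

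**2. The plan's own figures.** K.1 uses a two-sided pooled-variance z test, alpha 0.05, 497 per arm and 16% control mortality. Recomputed fixed-sample power is 0.900 for 9.19%, 0.850 for 9.65% and 0.800 for 10.03%, as tabulated. The P.4 boundaries (3.71030, 2.51142, 1.99302 at 1/3, 2/3 and 1) give a simulated alpha of 0.050 and power of 0.800 at the stated drift of 2.82089. The stated design reproduces.

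**3. Dilution.** Let f be the share of placebo patients already treated and b the fraction of the planned benefit that the earlier dose carries. Both are assumptions. TXA-arm risk is held at the 10% used in P.4.

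- Control risk: p_C = 0.16 − b × f × 0.06
- Difference: d = p_C − 0.10
- Drift: d / √(2 p̄(1 − p̄)/497), with p̄ the mean of the two risks

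For f = 10% and b = 1: p_C = 0.154, d = 0.054, p̄ = 0.127, standard error = √(2 × 0.127 × 0.873/497) = 0.0211, drift = 2.56.

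Power under the three-look plan, by simulation with the P.4 boundaries:

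| f | Difference, b = 1 | Power, b = 1 | Difference, b = 0.5 | Power, b = 0.5 |
|---|---|---|---|---|
| 0 | 6.00 points | about 80% | 6.00 points | about 80% |
| 2% | 5.88 | 78% | 5.94 | 79% |
| 5% | 5.70 | 76% | 5.85 | 78% |
| 10% | 5.40 | 72% | 5.70 | 76% |

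On K.1's 85% scenario (9.65% versus 16%, fixed sample, b = 1), power goes from 85.0% to 83.8%, 81.7% and 77.8% at the same shares.

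**4. Dose comparison.** Under H.3 the planned totals are 1 g (abbreviated), 1 + 1 = 2 g (standard) and 1 + 1 + 1 = 3 g (repeat). If the earlier open-label dose was 1 g (an assumption), these become 2, 3 and 4 g. An abbreviated-arm patient then has the standard-arm total, and a repeat-arm patient exceeds the planned maximum.

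**5. H.2.2 beside P.5.** One says who may enter and the other says when dosing may stop. Both can be followed. What neither covers is a contraindication already known at enrolment. As written, such a patient can be randomised, can meet P.5, and stays in the intention-to-treat set.

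**The case against.** The size is unknown and may be small. The documents give no share already treated, and enrolment must fall within 2 hours of injury. The treatment called proven is TXA after trauma center arrival, which does not show that referring hospitals give it. The calculation also holds TXA-arm risk at 10%, whereas Hypothesis 4B expects more drug to lower mortality, which would reduce the dilution. All of this stands. Extending the range to 20% would give about 63% power, but nothing in the documents points to a share that large.

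Short criteria modelled on the prior large trial and applied in transit are a defensible choice, and J.4 already separates scene from referral enrolment. That helps to examine the route, but the subgroup is exploratory and does not identify treated patients.

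Three stronger readings are tempting, and the documents do not support them:

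- **That prior TXA goes uncollected, or that staff would not see it.** N.2 collects referring-hospital interventions in general, N.1 draws on emergency and hospital records, and H.2.2 foresees review of outside documentation. Open-label drug is not blinded. The case report forms and Manual of Operations are not in the file. What can be said is that the protocol does not name TXA as an item to record.
- **That H.2.2 and P.5 contradict each other.** P.5 reads naturally as covering what arises or becomes known during administration, including the 8-hour infusion.
- **That some enrolled patients do meet P.5 at entry.** The documents show only that they can. P.5 itself speaks of a rare instance.

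**Conclusion.** The omission holds in both lists, and a clear route into the trial passes through it. Already-treated patients can be randomised, which weakens the primary contrast and blurs the 1, 2 and 3 g comparison.

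The illustrated loss is about 2, 4 or 8 percentage points of power at 2%, 5% or 10% already treated with full benefit, and about 1, 2 or 4 points with half the benefit. These figures rest wholly on the assumed share and benefit, with TXA-arm risk fixed at 10%. They show sensitivity and do not predict what happened. No stated sample-size figure is wrong.

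The contraindication point is secondary. H.2.2 is silent where P.5 is not, and the sponsor should reconcile the two sections. This review takes no position on the clinical rule.

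**What to change.** 1. Add to the exclusions in H.2.2 and the charter: tranexamic acid already given for this injury. Check it from the handover information available at enrolment, as for the other criteria.
2. Record non-study TXA by name, before enrolment under N.2 and after enrolment under N.3, with dose and time.
3. State that patients later found to have had it stay in the intention-to-treat set under J.5.
4. Have the sponsor reconcile H.2.2 with P.5 on contraindications known at enrolment.

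The cost is one checklist line, the named data fields and a protocol and charter amendment. The sample size stays at 497 per arm. The downside is a small loss of eligible transfer patients. If the sponsor prefers to keep such patients eligible, the data fields are still needed to show how many placebo patients were untreated.
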